Adverse Event Review 	Х	X 	Х	X 	Х	Х	Х	Х	X	Х
Concomitant Medications Review 	X	X	Х	Х	X	Х	Х	Х	х	Х
Subject Diary Review		X 	X 	X 	X 					

#### **APPENDIX 1 – TNIV-E-101 TRIAL PROCEDURES SCHEDULE**

Note: Procedures shaded in grey are performed via scripted telephone call.

 Vital signs to be captured pre-vaccination and between 30 to 60 minutes post-vaccination.

 Includes assessments for hematology (complete blood count [CBC] with hemoglobin, hematocrit, red blood cell [RBC] count, platelet count, and white blood cell [WBC] count with differential) and serum chemistry (alanine aminotransferase [ALT], aspartate aminotransferase [AST], total bilirubin, alkaline phosphatase, creatinine, and blood urea nitrogen [BUN]).

 Subjects will be asked to report any grade 3 solicited or unsolicited adverse event or SAE experienced since the last visit and may be asked to return to the clinic for an unscheduled visit to evaluate the event(s) at the Investigator's discretion.

[4] All adverse events and concomitant medications taken will be collected through Day 21; thereafter only MAEs, SAEs, and SNMCs and medications taken for these events will be collected.

 The subject diary will be reviewed by the investigator and collected at the Day 7 visit (Stage 1 subjects ONLY) or Day 21 visit (Stage 2 subjects ONLY).

 On Day 21, all Group A and B subjects will be administered a rescue injection with a licensed influenza vaccine, and all Group C subjects will be administered an injection of saline placebo to maintain trial blind. Subjects should be free of acute illness (defined as the presence of a moderate or severe illness with or without fever, or an oral temperature ≥ 38.0°C) in order to receive the second vaccination. Subjects presenting with an acute illness on Day 21 may return to the study site within the next 7 days to receive their 2nd vaccination. If a subject has experienced any AEs/SAE between study Days 0 and 21, then Day 21 vaccination may be administered or delayed for up to 7 days based on the Investigator's discretion.

 If needed, a physical examination may be performed, based on the investigator's discretion.

Nanoparticle Influenza Vaccine, Trivalent	Confidential	tNIV-E-101 Protocol
Novavax, Inc. Version	5.0 – 13 November 2017	Page 74

Trial Day:	0	3	7 (Stage 1 ONLY) 	7 (Stage 2 ONLY) 	21	56	90	182	273	364
Window (days):		±1	+1	±1	± 2	± 2	± 7	± 7	± 7	± 14

 Trial Procedures

 [8] All Stage 1 subjects will be required to complete a Day 7 in-clinic visit to present their subject diaries, whereas Stage 2 subjects will be required to complete a safety telephone call.

#### **Daily Diary Entries** \*\* GRADING FOR DIARRHEA 0 = Normal No noticeable symptom Subject ID Subject Initials Day of Vaccination Day 1 Day 2 Day 3 Day 4 Day 5 Day 6 Ongoing after Day 67 (Day 0) 1=Mild 1 to 3 unformed (loose) stools within a 24-hour period 2 = Moderate 4 to 3 unformed (loose) stools Date: Dates 1 i. 1 1 1 1 4 to 5 unformed (loose) stools within a 24-hour period 3 = Severe 6 or more loose stools within a 24-hour period, or requires intravenous hydration (tick the box if om is still cont after Day 6) ORAL TEMPERATURE o ap - F □ NO SYMPTOMS □ NO SYMPTOMS **NO SYMPTOMS** □ NO SYMPTOMS □ NO SYMPTOMS **NO SYMPTOMS** \*\*\* GRADING FOR NAUSEA AND VOMITING 0 = Normal No noticeable symptom 1 = Mild GENERAL SYMPTOMS 1 1 No interference with activity or Chills 1 to 2 episodes within a 24-hour period 2 = Moderate Muscle Patr Some interference with activity or >2 episodes within a 24-hour period 3 = Severe Joint Pain Severe Prevents daily activity or requires intravenous hydration Diarrhea Nausea 0 = NORMAL No noticeable symptom or finding Vomiting \*\*\* 1 = MILD Headache 0 Noticeable discomfort/pain, or symptom that does not interfere with activities of Fatique daily living RESPIRATORY/FACIAL SYMPTOM 2 = MODERATE Moderate discomfort/pain, or symptom that limits but does not stop activities of Cough daily living Difficulty Breathing 3 = SEVERE Chest Tightness Severe pain of symptoms that stop activities of daily living and may require medical treatment Wheezing Sore Throat Difficulty Swallowing Hoarseness Eye Redness Eyelid Swelling Facial Swelling INJECTION SITE SYMPTOMS 1 O = NORMAL No noticeable symptom Pain 1 = MILD MILD Noticeable discomfort or tenderness that does not interfere will normal activity. 0 Bruising\* Redness\* 2 = MODERATE Moderate discomfort or tenderness t swelling\* casuses some limitation of normal activity Please complete the questions below by choosing either "Yes" or "No." Circle your response Any box marked with a "YES" will require additional information/explanation. 3 = SEVERE SEVERE Severe pain at rest, immobilizes the injected arm and prevents normal daily activity Have your medications changed or are you taking any new medications? VES NO YES NO YES NO YES NO VES NO YES NO YES NO SEE SUBJECT MEASUREMENT TOOL If yes, please record in the Medication Log INSTRUCTIONS Did you visit a doctor? YES YES YES NO YES YES YES NO YES NO NO NO NO NO If yes, please record the reason for seeking medical attention in the Doctor Visit Log Did you have any other symptoms? YES YES NO YES YES NO YES NO NO YES NO YES NO If yes, please list them in the "Other NO Symptoms Log " on page 8.

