## 3.1.1.1 Vaccination Holding Rules

Adverse event reports meeting any one of the following 2 criteria will result in a hold being placed on subsequent enrollment and vaccinations, pending further review by the independent medical monitor and sponsor:

- 1) The occurrence of at least 1 serious adverse event among any Stage 1 subject assessed by the sponsor as definitely related to the trial treatment.
- The occurrence of any severe (grade 3) solicited (local or systemic) adverse event term in > 10% of all Stage 1 subjects.

If vaccination holding rules are met at any review point, the independent medical monitor will:

- 1) Review a summary of all individual data of the relevant subject(s), including the unblinded treatment assignment, and summary safety data relative to all treatment groups; and
- 2) If there exists any imbalance that is higher in one of the two Tri-NIV treatment groups compared to the Fluzone HD group, review a detailed accounting from the investigator(s) as to the exact nature of the clinical symptoms or physical findings in the subject(s) triggering the holding rule, including any potential causation and evidence of resolution with or without treatment.

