Standard severity grading definitions will be provided in the diary. Grading of visible, measurable injection site reactions will be based on the Food and Drug Administration (FDA) Guidance for Industry, Toxicity Grading Scale (TGS) for Healthy Adult and Adolescent Volunteers Enrolled in Preventive Vaccine Clinical Trials (September 2007). Definitions are summarized in Table 5. Oral temperatures will be collected as a continuous variable and graded by the investigator based on ranges provided in the TGS as shown in Table 6.

Investigators will not be required to assess causality of solicited adverse events specifically named in the diary if onset is during the solicitation period (these will be presumed to be treatment-related). Adverse events consistent with the solicited adverse events listed in the diary, but with onset after the solicitation period (ie, Day 7 thereafter), will be captured as unsolicited AEs and are subject to all procedures for unsolicited AE data.

Solicited AEs, collected from the subject diary, which continue after the collection period (ie, on or after Day 7 for vaccination-emergent events) will be followed to resolution. The continuing, solicited AE will be captured by verbatim term on an "AE eCRF" page. The investigators will be required to assess severity of the continuing solicited adverse event(s) starting from the time after the last diary entry until resolution.

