# 8.4 Severity

All AEs will be assigned severity by the subject and/or investigator (as applicable) according to the TGS. Subjects will also be able to indicate severity for any AEs experienced and record this in their diary according to the same scale. For quick reference, an abbreviated grading scale is provided in Table 5 for visible and non-visible local AEs and for systemic AEs for which severity is based on interference with daily activities and not numeric ranges, and in Table 6 for fever and gastrointestinal adverse events of nausea, vomiting, and diarrhea.

The severity of visually-evaluated local AEs will be a function of size. During the diary period, subjects will monitor the size of visible local AEs at the injection site using the Subject Measurement Tool (Appendix 4) which has concentric circles that correspond to the diameters specified in Table 5. For the purposes of reporting during the solicitation period (ie, Day 0 through 6, inclusive) the subjects' observations will form the primary data. During clinic visits, investigators may measure any persisting local AEs with a ruler, documenting the size of the reaction at its widest diameter, using the numeric scale provided in Table 5 to assess for severity.

Systemic solicited AEs and unsolicited AEs will be assigned a severity grade based primarily on disruption of normal daily activities, with the exception of fever and select solicited gastrointestinal AEs that have their own distinct toxicity grades (Table 6). Medical care-seeking is typically absent for grade 1 (mild) and often present for grade 3 (severe) events, but is not the primary determinant of severity, since individuals behave differently in this regard.

Severity of vital sign abnormalities (including oral temperature, which is captured as a continuous variable) will be graded based on established ranges provided in the TGS and reported as an AE using the criteria outlined in Section 8.1.3.

	Definitions for Local Adverse Events		Definitions for Systemic Adverse Events
Severity Grade	Visual Local AE Size Grading Description	Non-Visual Local AE Grading Description	Systemic AE Grading Description
0 – Normal	Reaction size (greatest single diameter) < 2.5 cm	No noticeable symptom	No noticeable symptom or finding

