1 - Mild	Reaction size (greatest single diameter) 2.5 to 5.0 cm	Discomfort or tenderness noticeable, but does not interfere with normal daily activities	Mild symptoms or diagnostic observations; intervention not indicated; no interference with normal activity
2 – Moderate	Reaction size (greatest single diameter) > 5.0 to 10.0 cm	Moderate discomfort or tenderness on firm pressure; causes some limitation of normal daily activities	Moderate symptoms or diagnostic observations; some interference with normal activity, not requiring medical intervention
3 – Severe	Reaction size (greatest single diameter) > 10.0 cm	Severe pain at rest, pain or tenderness immobilizes the injected limb and prevents normal daily activities	Severe symptoms, significantly disrupts or prevents normal daily activities, generally requires medical attention/intervention

Table 5:	Definition of Severity Grading for Adverse Events
----------	--

Table 6:	Severity Grade Definitions for Solicited Gastrointestinal Adverse Events and Fever
----------	--

	Gastrointestinal Adverse Event			
Severity Grade	Nausea Vomiting Diarrhea		Fever	
0 – Normal	No noticeable symptom	No noticeable symptom	No noticeable symptom	< 38.0
1 – Mild	No interference with activity, or 1	No interference with activity, or 1	1 to 3 unformed (loose)	38.0 to 38.4

	Gasti			
Severity Grade	Nausea Vomiting		Diarrhea	Fever
	to 2 episodes/ 24-hour period	to 2 episodes/ 24-hour period	stools/24-hour period	
2 – Moderate	Some interference with activity, or > 2 episodes/ 24-hour period	Some interference with activity, or > 2 episodes/ 24-hour period	4 to 5 unformed (loose) stools/24-hour period	38.5 to 38.9
3 – Severe	Prevents daily activity, or requires intravenous hydration	Prevents daily activity, or requires intravenous hydration	≥ 6 loose stools/24-hour period, or requires intravenous hydration	> 38.9

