#### **APPENDIX 4 – TNIV-E-101 SUBJECT MEASUREMENT TOOL**

(Do not use this page in clinic, as it may not be to exact scale)

The Subject Measurement Tool consists of a transparent set of concentric circles with diameters that correspond to the ranges in the toxicity grading scale (2.5, 5, and 10 cm, in diameter). Subjects are instructed to overlay the template over the injection site for any reaction that can be visually observed (eg, redness, swelling, bruising). An assessment of severity is then made by determining the circle that best describes the size of the reaction: reactions that are smaller than Circle A (2.5 cm) are considered Grade 0; reactions larger than Circle A but equal to or smaller than Circle B (5 cm) are considered Grade 1; reactions larger than Circle B but equal to or smaller than Circle C (10 cm) are considered Grade 2; reactions larger than Circle C are considered Grade 3. The table below summarizes the severity grading for visible injection site reactions based on size.

Severity Grade	Injection Site Grading Description
0 - Normal	Reaction size fits inside Circle A
1 - Mild	Reaction size larger than Circle A, but fits inside Circle B
2 - Moderate	Reaction size larger than Circle B, but fits inside Circle C
3 - Severe	Reaction size larger than Circle C

Definition of Severity Grading for Visible Local Adverse Events

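### The draft diary sets systemic Grade 3 more narrowly than Table 5, so Grade 3 can be under-recorded for 15 of 23 solicited terms if that wording is issued

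*Protocol*

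**What the plan says.** Protocol Section 8.4 lets subjects grade any event they have and "record this in their diary according to the same scale". The scale is the toxicity grading scale, abbreviated in Tables 5 and 6. Section 8.1.1 adds: "Standard severity grading definitions will be provided in the diary".

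For systemic events, Table 5 defines Grade 3 as "Severe symptoms, significantly disrupts or prevents normal daily activities, generally requires medical attention/intervention". Its Grade 2 includes "some interference with normal activity, not requiring medical intervention".

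The draft diary in Appendix 2 has its own key for general and respiratory/facial symptoms. Grade 3 is "Severe pain of symptoms that stop activities of daily living and may require medical treatment". Grade 2 includes a "symptom that limits but does not stop activities of" daily living. A note to the appendix says that this is a sample and that the diary given to subjects may differ.

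Grade 3 solicited terms also drive safety decisions. Under Section 3.1.1.1 one trigger for a hold is "The occurrence of any severe (grade 3) solicited (local or systemic) adverse event term in > 10% of all Stage 1 subjects". Section 3.1.1.2 applies the same proportion to all subjects in roughly weekly tabulations.

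SAP Section 8.1 says solicited severity is graded by definitions in the protocol and in the subject diary, without saying which governs. SAP Section 8.1.1 reprints the protocol's Tables 5 and 6 as SAP Tables 4 and 5.

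For visible reactions, Table 5 starts Grade 1 at 2.5 cm. The table in Appendix 4 describes Grade 0 as "Reaction size fits inside Circle A", and Circle A is 2.5 cm across.

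**The concern.** Table 5 offers two routes to systemic Grade 3 on activity: significant disruption, or prevention. The draft diary keeps only the second and puts everything short of it in Grade 2. A subject whose headache or fatigue badly disrupts the day without stopping it has a Grade 3 event by Table 5 and a Grade 2 event by the diary.

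No step in the documents brings such an entry back to Table 5. Under Section 8.1.1 the diary offers the severity grades to the subject. The investigator grades temperature, and grades continuing events only from the time after the last diary entry. The investigator reviews the diary, but no instruction to regrade is given. The Day 3 and Stage 2 Day 7 calls ask about Grade 3 events, and the definition the subject holds is the diary's.

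Two things are at stake. Solicited events are a primary endpoint and are tabulated by severity, so diary grades could appear under Table 5 labels. The same grades decide whether a first-in-human trial pauses.

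**Working it through.** The plan gives no figure of its own here. The check sets the definitions side by side, counts the terms affected, and then shows how the hold rule would respond under assumed values.

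**1. Definitions compared**

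| Item | Protocol Tables 5 and 6 | Draft diary or tool | Same? |
|---|---|---|---|
| General and respiratory/facial, Grade 3, activity | significantly disrupts, or prevents | stops | No, the diary is narrower |
| Same, medical care | generally required | may be required | No, the diary is looser |
| Injection-site pain, Grade 3 | severe pain at rest, limb immobilized, activity prevented | essentially the same | Yes |
| Nausea, vomiting, diarrhea | Table 6 | matches Table 6 | Yes |
| Fever | numeric ranges | recorded as a temperature, graded by the investigator | Yes |
| Visible reaction, Grade 3 | over 10 cm | larger than Circle C (10 cm) | Yes |
| Visible reaction of exactly 2.5 cm | Grade 1 | Grade 0 by the Appendix 4 table; unassigned in its text | No |

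The two differences in the systemic rows do not cancel. Section 8.4 bases systemic severity mainly on disruption of daily activity and says that seeking care is not the main determinant. The criterion that is narrower is the one the protocol puts first.

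**2. Terms affected (protocol Table 3)**

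- Local 4 + general 6 + gastrointestinal 3 + respiratory/facial 10 = 23 terms.
- Affected: the general terms other than temperature (chills, muscle pain, joint pain, headache, fatigue) = 5, plus 10 respiratory/facial = 15.
- Not affected at Grade 3: temperature 1 + gastrointestinal 3 + local 4 = 8.

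**3. Size rules at the boundaries (Table 5 grade / Appendix 4 table grade)**

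2.4 cm 0/0; 2.5 cm 1/0; 2.6 cm 1/1; 5.0 cm 1/1; 5.1 cm 2/2; 10.0 cm 2/2; 10.1 cm 3/3. The tool differs only at exactly 2.5 cm and never at Grade 3.

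**4. Hold rule, illustration only**

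- Stage 1 has about 60 subjects (Section 3.1). More than 10% of 60 is more than 6, so at least 7 subjects must have the same Grade 3 term.
- Let p be the Table 5 Grade 3 rate for one affected term, pooled over all three arms. Let f be the share of those events recorded as Grade 2 because of the diary wording. Neither value is in the documents; both are assumed.
- Recorded rate: q = p(1 − f).
- P(trigger) = P(X ≥ 7) = 1 − Σ(k = 0 to 6) C(60, k) q^k (1 − q)^(60 − k), with X binomial(60, q).
- Example: p = 15%, f = 25% gives q = 0.15 × 0.75 = 11.25%; f = 50% gives q = 7.5%.

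| p | f = 0 | f = 10% | f = 25% | f = 50% |
|---|---|---|---|---|
| 5% | 3.0% | 1.8% | 0.7% | 0.1% |
| 10% | 39.4% | 29.4% | 16.1% | 3.0% |
| 15% | 81.5% | 71.7% | 51.9% | 16.1% |
| 20% | 96.9% | 93.3% | 81.5% | 39.4% |

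The loss is large only where the true pooled rate is at or above the 10% threshold and f is not small.

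**The case against.** The strongest reply is that Appendix 2 is only a draft. It says the issued diary may differ, and Sections 8.1.1 and 8.4 already require the standard definitions and the same scale. This stands as far as it goes. A reader might infer that severe events are in fact under-counted, but the documents do not show the issued diary, so they cannot support that. The inconsistency remains: protocol version 5.0 still carries the draft wording and shows no other.

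Second, the illustration depends on its inputs. Section 1.9 reports severe solicited events in 0 to 4% of subjects after one Matrix-M1-adjuvanted dose of another antigen, and in about 1 to 2% after an unadjuvanted one. Near those rates the rule seldom fires under either wording. A reader who takes only the fall from 81.5% to 16.1% would overstate the risk. This stands, and it is why the 5% row belongs beside the 15% row. It does not remove the effect on the severity tables, where the recorded rate falls by the share f at any base rate.

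Third, a reader might infer that every difference lowers the grade, or that the 2.5 cm point also weakens the hold. Neither follows. The medical-care wording is looser in the diary, eight terms have essentially the same Grade 3 definition, and the 2.5 cm point lies on the Grade 0/1 boundary. The Appendix 4 text also agrees with Table 5 that smaller than 2.5 cm is Grade 0, so only exactly 2.5 cm is in doubt.

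Fourth, the sentence in Section 8.4 that makes subjects' observations the primary data sits in the paragraph on visible local reactions, and should not be stretched to all solicited events. Section 8.4 allows grading by subject or investigator as applicable, and there are calls, a Stage 1 clinic visit and diary review. These contacts could catch some events, but none is described as regrading entries to Table 5. SAP Tables 4 and 5 do reprint the protocol scale, but SAP Section 8.1 also cites the diary and sets no precedence.

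Finally, all arms use the same diary, so the wording brings in no arm-specific grading rule. That is correct. The issue is how recorded grades compare with the protocol's scale and with a fixed threshold.

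**Conclusion.** The protocol promises one scale and shows two for systemic symptoms. If the draft diary is issued as written, Grade 3 can be under-recorded against Table 5 for 15 of 23 solicited terms, in the primary severity tables and in the counts for the hold and suspension rules. The direction follows from the activity criterion. The size does not, because the documents give no share of events that disrupt activity without stopping it.

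Under assumed shares of 25% or 50%, the Stage 1 trigger chance for a single term falls from 3.0% to 0.7% or 0.1% at a pooled rate of 5%, and from 81.5% to 51.9% or 16.1% at 15%. This assumes 60 independent subjects with a common rate. An actual under-count is not established.

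The 2.5 cm mismatch is a separate, minor point with no bearing on Grade 3.

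**What to change.** - Before diaries are issued, reconcile the Grade 1 to 3 wording for general and respiratory/facial symptoms in Appendix 2 with Table 5, so that both give the same grade to a symptom that significantly disrupts activity without stopping it.
- If diaries are already out, document which wording they carry and report it with the solicited-event tables and the hold-rule tabulations. If the wording is replaced during enrollment, record which subjects used which version.
- In SAP Section 8.1, state that protocol Tables 5 and 6 (SAP Tables 4 and 5) are the governing scale. This sentence alone does not regrade entries made under other wording, so it does not replace the first two steps.
- As a minor edit, have Appendix 4 assign a reaction of exactly 2.5 cm to the same grade as Table 5, in both its text and its table.

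The cost is a few lines of diary, tool and SAP text before printing, or a replacement diary page notified to the IRB if diaries have been issued. Sample size, visits and the hold threshold do not change.

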
#### **APPENDIX 2 – TNIV-E-101 SUBJECT DIARY CARD (DRAFT)**

\*A subject diary will be provided to all subjects to record solicited and unsolicited adverse events experienced, concomitant medications used, and any medical visits/procedures sought, within the first seven days following Day 0 vaccination. The above is a sample excerpt from such a diary. It is provided for informational purposes only and may differ from the actual diary issued to subjects.

#### **APPENDIX 3 – TNIV-E-101 BLOOD DRAW SCHEDULE**

Trial Visit Day	Amount of Blood Drawn for Immunogenicity Assessment (mL)	Amount of Blood Drawn for Clinical Safety Assessment (mL)
Day 0 (pre-vaccination)	20	10
Day 21 ( $\pm 2 days$ )	20	10
TOTAL FOR ENTIRE TRIAL (mL)	6	0

